### 1. \* Protections when conducting one-on-one in-person interventions or interactions (for groups see Q2 below):

- Conducting study activities in locations that maximize privacy (limited people around, closing doors, drawing drapes around beds, monitoring voice volume, etc.)
- Verifying identity before discussing personal information.
- Asking the participant if they are comfortable answering questions in that location
- Asking the participant if they are comfortable with having other people present (if any)
- Moving away from other people when conducting activities in public spaces or offering a private space
- Offering other options of ways to respond to sensitive questions (i.e. pointing, clicking, or writing) if uncomfortable verbally responding
- Using generic signs on research rooms and spaces, particularly for research on stigmatizing or sensitive topics
- Other protections not listed in this question – describe below
- N/A – study has no in-person interventions or interactions with participants

### 2. \* Protections when conducting group interventions or interactions:

- Conducting study activities in locations that maximize privacy (limited people passing by, closing doors, monitoring voice volume, etc.)
- Moving to a more private area to answer questions or to discuss concerns
- Discussing privacy with the participants and the importance of not talking outside the group about what other people say during the group session
- Allowing participants to use a pseudonym or limiting use of individuals' names during the group activity
- Asking everyone in a public group setting (e.g. classrooms, workshops) to turn something in (blank or filed) so participants do not have to self-identify when turning in materials
- Collecting paper forms in a closed box or envelope rather than passing to others or leaving in an open area
- Limiting participant identifiers that would be visible on paper documents (i.e. using study IDs instead of direct identifiers)
- Allowing people to distance themselves from other participants during group activities
- Offering other options of ways to respond to sensitive questions (i.e. pointing, clicking, or writing instead of speaking)
- Using generic signs on research rooms and spaces, particularly for research on stigmatizing or sensitive topics
- Ensuring non-participating individuals are not captured on recordings or in photos
- Other protections not listed in this question – describe below
- N/A – study has no group interventions or interactions

### 3. \* Protections when conducting remote interventions or interactions (e.g. phone, text, email, video-conference, tele-health, online, etc.):

- Conducting study activities in locations where study staff can maximize their own privacy (limited people around, closing doors, monitoring voice volume, etc.)
- Leaving/sending generic messages that avoid using study and participant identifiers, such as names, study titles, clinics, study topics, etc.
- Obtaining permission prior to sending text messages
- Advising the participant to move to a location where they are comfortable answering questions and will not be overheard
- Advising online participants to complete the activity at a time and location where they will be comfortable answering questions
- Ensuring non-participating individuals are not captured on recordings or in photos
- Offering other options of ways to complete the activity (i.e. online, paper, phone) if more privacy is desired
- Offering a way to save and return later to the online activity if privacy is compromised
- Other protections not listed in this question – describe below
- N/A – study has no remote interventions or interactions with participants

### 4. \* Protections when mailing study materials to/from participants:

- Obtaining permission to mail study materials
- Confirming/verifying the accuracy of addresses before mailing items
- Ensuring the participant is able to personally receive mailed materials and has a way to protect their own privacy if they do not want others to know they are receiving research communications (i.e. notifying participants of when to expect it)
- Using return address labels and document headers that avoid study identifiers, such as study names, clinics, study topics, etc.

- Avoiding or limiting use of participant identifiers and health information on mailed documents (i.e. using study IDs instead of direct identifiers)
- Providing a return mailing address label or pre-addressed envelope to ensure returned items are sent to the correct address
- Communicating receipt of mail from participants and/or asking them to notify you when they mail it to ensure study documents are not lost in transfer
- Offering other options of ways to complete the activity (i.e. by phone or online) if desired
- Other protections not listed in this question – describe below
- NIA – not mailing any materials to/from participants

6. \* Protections when analyzing or disseminating study data \*Applicable to all studies\*:

- Working only in locations where the study team can ensure privacy (not working in close proximity to non-study personnel, closing doors, closing/putting away documents/files before leaving, etc.)
- Securing physical materials only in locations that ensure privacy (access limited to authorized study personnel)
- Only sharing data/specimens in accordance with the Sharing Plan outlined in this smartform
- Obtaining explicit parental permission before disseminating or sharing recordings or photos of children
- Blurring/redacting/hiding faces and other identifiable features/marks (tattoos, scars, birthmarks, distinctive voice, etc.) in recordings or photos prior to disseminating or sharing
- Only publishing or presenting aggregate results or findings (i.e. no individual-level information)
- Taking additional steps to protect participant identities when publishing or presenting individual-level information, quotations, results, images – describe below
- Other protections not listed in this question – describe below

8. Describe any other way(s) that the research team will protect participants' privacy. See the help text for additional guidance.

All patient interactions will be done in a private examination room or practitioner offices at the Stony Point Ambulatory Center, ACC clinics, NOW center (Short Pump) or the perisurgical areas. These offices are all private, with doors that close. No patient will be approached in the waiting area. No images will be taken.

Once data collection is complete, all data will be de-identified and there will be no risk to the patient. Prior to de-identification, all data will be housed on a password protected computer in a locked office at the VCU Medical Center (within RedCap).

All patients (whether receiving the active injection or the placebo) will have the injection prepared in the investigational pharmacy and delivered to the OR either the day prior to or the morning of the surgery. The labels on the syringes will not note the treatment group, thus keeping the blinding. This is the only research activity while the patient is hospitalized. After the surgical procedure, all activities will be standard post-op treatment. The research activity will occur later via chart review (mg of pain medicine)

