## Study Population

1. Provide the maximum number of individuals that

1. May participate in any study interaction or intervention (including screening, consenting, and study activities)

AND/OR

2. You obtain any data/specimens about (regardless of identifiability)

at VCU and at other sites under the VCU IRB's oversight. See the help text for additional guidance.  
200

2. If this is a multi-center project, what is the maximum anticipated number of subjects across all sites?  
NA

3. Provide justification for the sample size by explaining how you arrived at the expected number of participants and why this number is adequate for answering the research questions:  
Power established from a previous pilot study. A previously-approved (institutional review board) pilot study was performed to identify the number of patients needed to obtain sufficient power. Using a reduction in pain score of 50%, alpha of 0.05 and a power of 90%; a sample size of 64 in each group is necessary. The pilot study found that the pain scores were essentially equal by approximately 24 hours, therefore power was calculated for comparison up to about 12 hours postoperatively.

This is also referenced in the research methods section.

The final sample size was determined by the above power analysis and increasing to 200 to account for screen failures.

4. List the study inclusion criteria:

Patients 18 years of age and older, scheduled to undergo a total knee arthroplasty, able to provide informed consent. Patients must receive Duramorph intrathecally.

5. List the study exclusion criteria:

Under the age of 18, using 80 morphine equivalents of narcotic pain medication preoperatively, had a history of allergic reaction to any of the medications used in the study, had creatinine clearance of less than 60 mL/min, currently pregnant, a BMI > 40 and a weight < 75kg. Patients unable to consent in English may be included by using the VCU language services to translate the consent. This population has traditionally been very low in the population that is being offered the study though, so it isn't anticipated to be needed. Patients will not be included if they are allergic to any of the study medications: ropivacaine, clonidine, ketorolac, or epinephrine.

6. Will individuals with limited English proficiency be included in or excluded from this research?

Included

Excluded - safety concerns if participants are unable to communicate with the study team

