**See the help text for additional guidance.**

Patients will be recruited at either the NOW center (Short Pump), Stony Point Outpatient Clinic or the Ambulatory Care Center clinics. Patients will be informed of the study once he/she has elected to undergo a total knee arthroplasty and has signed a consent for that procedure. If interested in joining the study, they will be given an informed consent to review and sign. The study will only be offered to those patients that have already signed a consent for the knee arthroplasty procedure.

The attending physicians who have made the decision that a TKR is medically necessary will determine if a patient is eligible.

The Orthopedic department has multiple studies being done in patients undergoing a TKR. Some of the studies have priority over others. Once it has been determined which studies a patient is being offered, they will be given a consent and it will be reviewed by the current orthopedic fellow. In the interest of improving our subject recruitment, some patients may be called via telephone to discuss the study. (see attached script). The actual consent will be reviewed and signed prior to surgery in the perioperative area where the patient will also have the opportunity to ask any further questions.

The fellow may also review the study to all eligible patients at their medical appointments (these occur approximately one month prior to surgery). As noted previously, they will be given this information in a private examination room and given time to ask questions and/or to take the ICF home and peruse it. Any questions can be directed to the fellow. This is all done once the decision has been made to perform a TKR.

5. **Does this study have a separate protocol document (i.e. a multisite or sponsor's protocol) that contains a detailed description of the study's methodology?**

- Yes
- No

6. **Since a separate protocol document is not uploaded, describe the proposed research using language understandable to those IRB committee members whose expertise is not scientific. The description must include:**

1. A statement explaining the study design
2. A detailed description of all the procedures that will be followed to carry out the study, preferably in sequential order, and in sufficient detail that the study's methods could be replicated
3. A description of all research measures/tests/interventions that will be used (if applicable)

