**Randomization:**

Each patient will be randomized to one of two groups: intrathecal morphine with intraoperative periarthicular injection using a "joint cocktail" (treatment group) and intrathecal morphine with a placebo injection (placebo group) for perioperative pain management. A randomization schedule created by the pharmacy prior to the study will be used to determine to which treatment group each patient will be assigned. The pharmacists will prepare either injection and transport to the OR during each patient's procedure. The treatment group will receive an injection of 50 mL of 0.5% ropivacaine, 0.8 mL (0.1mg/mL) clonidine, 1 mL (30 mg/mL) ketorolac, 0.5 mL (1 mg/mL) epinephrine, and 47.7 mL 0.9% saline for a total volume of 100 mL. The patients in the placebo group will receive 100 mL of 0.9% saline.

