#### MONITORING PROCEDURES

[name] assures that informed consent is obtained prior to performing any research procedures, that all subjects meet eligibility criteria, and that the study is conducted according to the IRB-approved research plan.

Study data are accessible at all times for the PI and co-investigators to review. The PI and co-investigators review(s) study conduct including accrual, screen failures, protocol deviations on a quarterly basis. The PI and co-investigators review AEs individually in real-time and in aggregate on a quarterly basis. The PI and co-investigators review(s) serious adverse events (SAEs) in real-time. The PI ensures all protocol deviations, AEs, and SAEs are reported to the IRB according to the applicable regulatory requirements.

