**7. \* Describe the consent procedures used for this group. Address each point below:**

- When and where consent will occur
- What will be covered during the consent discussion
- How the consent discussion will occur (e.g. in-person, phone, video conference)
- How you will reconfirm consent on an ongoing basis, if applicable

Consent (research) will be obtained after the patient has signed the consent for the knee arthroplasty. Once this is signed the patient will be approached by the surgeons or coordinators to offer this study. This will occur in a private office or examination room at Stony Point, ACG clinic, the NOW clinic or the perioperative area.

**8. Select the processes for minimizing any potential perception of undue influence to participate, particularly when there is a pre-existing relationship between the participant and the researcher (e.g. treatment provider/patient; instructor/student; supervisor/employee, etc.):**

- Having a 3rd person (family/friends, another study team member, etc.) present during the consent / assent discussion
- Having an independent advocate (e.g. advocate for decisionally impaired adults, wards) present during the consent / assent discussion
- Removing physical symbols of authority like white coats or police badges
- Sitting down beside the participant instead of standing over them
- If obtaining consent / assent in a clinical setting, letting patients sit instead of lie down (if they are able to)
- Moving to a more neutral location like a conference room
- Obtaining consent / assent after other services/interactions have been completed (e.g. after school or the clinic visit)
- Having a mandatory wait period for the participant to go home and think before they sign consent / assent
- Sharing the consent / assent discussion between two people (i.e. a clinician might be the best person to explain study procedures and risks, but then they could step out and let a research assistant finish the consent process)
- Other protection(s) not listed here – describe below
- N/A: Requesting Waiver of Consent

8. Describe the other ways the study team will minimize any potential perception of undue influence to participate:  
 No coercion will occur; patients will be told that if they do not agree to participate, they will get the standard of care joint injection.

10. How much time will participants be given to make a decision:  

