 The time period to make a decision will be a matter of weeks to months. The study will be presented to patients once a decision has been made to undergo a TKR (consent has been signed). The time period between surgery decision and surgery is variable and patient specific—but there is adequate time to make a decision

11. If applicable, describe the procedures for consenting children upon entering adulthood or participants who are no longer decisionally impaired:  
 N/A

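### Do the two delivery times for the study injection mean that patients are allocated before they sign consent?

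*Combined protocol and SAP*

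**What the plan says.** Two places describe how the injection reaches the operating room.

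- Study Procedures, under Randomization: "The pharmacists will prepare either injection and transport to the OR during each" patient's operation. The arm comes from a schedule that the pharmacy drew up before the study. One arm receives a four-drug mixture made up to 100 mL, the other 100 mL of saline.
- Privacy page, last free-text answer: for both arms the injection is "delivered to the OR either the day prior to or the morning of the surgery", with syringe labels that do not show the arm. Shortly afterwards comes the sentence "This is the only research activity while the patient is hospitalized".

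Three places bear on consent.

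- Study Procedures, recruitment answer: "The actual consent will be reviewed and signed prior to surgery in the perioperative area". This follows directly on a sentence about patients who are telephoned.
- Consent Groups, consent procedures: the approach takes place "in a private office or examination room at Stony Point, ACG clinic, the NOW clinic or the perioperative area". On time to decide: "The time period to make a decision will be a matter of weeks to months".
- Monitoring Procedures: a named member of the team assures that "informed consent is obtained prior to performing any research procedures, that all subjects meet eligibility criteria".

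**The concern.** The delivery times cannot both describe the same syringe. If the word for during governs only the transport, the arrival times still differ, and preparation can never be later than delivery.

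The mismatch would matter through the order of allocation and consent. Making up an arm-specific syringe uses up a place on the schedule. If that happens the day before surgery and the patient signs in the perioperative area the next day, the patient has been allocated without having consented. On its face this conflicts with the consent-first rule in the Monitoring Procedures.

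A patient who then declined, or proved ineligible, would be allocated but never injected. The Randomization and Privacy text gives no rule for that patient's number or syringe. The possible costs are an unclear moment of randomisation, avoidable exclusions after allocation, and a departure from the schedule if the syringe went to the next patient.

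**Working it through.** The plan gives no figure on this point, so the check is one of sequence. Cross the two kinds of signing with the three delivery times. One assumption is needed: a signature in the perioperative area falls on the day of surgery. That is the natural reading, but the documents do not state the day.

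| Research consent signed | Delivered the day before | Delivered that morning | Transported during the operation |
|---|---|---|---|
| In clinic, ahead of surgery | consent first | consent first | consent first |
| Perioperative area, day of surgery | allocation first | order not determined | consent first, if preparation also waits |

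Of the 2 × 3 = 6 combinations, 3 put consent first without condition and 1 does so if preparation waits. In 1 the order is open, and in 1 allocation necessarily comes first. No sentence authorises that last combination. It appears only when one option from the Privacy page is paired with one consent location from elsewhere. The Privacy page offers alternatives, and these fit a simple practice: day-before delivery for patients who have already signed, later delivery for the others. The consent-first rule points the same way.

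Next, suppose the adverse combination did occur.

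1. **Bias.** The pharmacy holds the schedule, the labels do not show the arm, and the trial is double blind. Neither the patient who declines nor the team that judges eligibility knows the arm. Loss between allocation and injection is therefore unrelated to arm, and the comparison among injected patients remains a randomised one.
2. **Schedule.** Passing an unused syringe to the next patient would depart from the list. It would not reveal the next assignment to those who enrol patients, so it opens no route to selection.
3. **Numbers.** The requirement is 2 × 64 = 128 patients. The ceiling is 200, raised above 128 to allow for screen failures. It is not a pure reserve, because it also counts people who are only screened or approached. Even so, losing a place before injection does not by itself cut the number analysed below 128. The documents give no refusal rate and no split between clinic and perioperative signing, so no power figure can be derived.

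**The case for a change.** The strongest case for a change is that this document is the whole protocol. The form says that no separate one exists and asks for steps that could be replicated. Nothing in the available text ties release of an allocation to a signature, or says what happens to a syringe made up for someone who declines. Such a patient has been told to expect the standard joint injection, while an unlabelled study syringe may already be in the operating room. Weeks to months is time to decide and does not fix the time of signing. The Privacy page also appears to call the syringe step research activity, which would bring it under the consent-first rule.

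Part of this stands. The two delivery times do disagree, and the link between signature and allocation is left to practice.

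The rest is weaker. In "This is the only research activity while the patient is hospitalized" it is unclear whether the first word means the pharmacy's work or the injection itself, and the phrase is limited to the time in hospital. Work done the day before, for a patient who arrives on the day of surgery, is not clearly covered. If the work is covered, the consent-first rule forbids doing it before signature, so the plan already excludes the sequence.

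A related worry is that receipt of the spinal drug ("Patients must receive Duramorph intrathecally") might not be known when the syringe is made up, and that the analysis population is unclear. This cannot be held against the plan, because the methods narrative breaks off in the available text just after the heading Preoperative Intervention.

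**Conclusion.** No change is needed. The discrepancy is a clerical slip between a methods paragraph and a privacy answer. The missing step, drawing the allocation once consent is signed and eligibility confirmed, is one that the Monitoring Procedures already imply and that a pharmacy and study team would apply. Aligning the two sentences would be housekeeping and would alter no estimate, test or conclusion.

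The effect on the result is none that can be shown: no bias, no demonstrated loss of power, and an affected group that the documents do not allow anyone to size. The documents also do not show that any patient was allocated before consent.

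This rests on three assumptions: the team observes its consent-first rule, the blind holds up to the injection, and the pharmacy alone holds the schedule. If the arm became known to those obtaining consent before the patient signed, the argument that late refusals are unrelated to arm would fail. Nothing in the documents suggests that it does.
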